2.3. Benefit/Risk Assessment

While there were no clinical data available for IW-3300 at the outset of this first-in-human study, available nonclinical data with IW-3300 support a favorable risk/benefit profile. When administered orally, GC-C agonists may cause diarrhea and dehydration. This should be minimized in this study as IW-3300 is being administered intrarectally as a low-volume enema. More detailed information about the known and expected benefits and potential risks of IW-3300 may be found in the [IB](#).

2.3.1. Risk Assessment

Potential Risk of Clinical Significance	Summary of Data/Rationale for Risk	Mitigation Strategy
Study Intervention: IW-3300		
Potential for diarrhea and secondary dehydration	These are class effects of GC-C agonism or effects observed in nonclinical safety pharmacology and toxicology studies of IW-3300.	Intrarectal administration will likely decrease the risk of diarrhea and subsequent dehydration. The study design includes dose escalation to closely monitor subject safety and tolerability at each dose level before dosing with a higher dose; a Dose Escalation Committee will conduct blinded reviews of all the safety parameters of the dosing cohort through Discharge (Day 2) in order to make decisions regarding escalation to the next dose. Orthostatic vital sign measurements will be taken to evaluate the potential for volume depletion. The daily BM frequency and stool consistency will be monitored in real time to evaluate changes in bowel habits and the potential risk of diarrhea. Stopping rules will also be in place to evaluate continued dosing (Section 7.1.1); dosing within a cohort may be temporarily suspended in the event of a diarrhea or dehydration serious adverse event (SAE); ≥ 1 subject with Grade 3 diarrhea (increase from baseline of >7 stools per day and/or watery stools [BSFS score of 7] resulting in a limiting of self-care activities) or dehydration (hospitalization indicated); or ≥ 2 subjects with Grade 2 diarrhea (increase from baseline of 4 to 6 stools per day and/or watery stools [BSFS score of 7] resulting in a limiting of instrumental activities) or dehydration (intravenous fluids indicated).

Potential Risk of Clinical Significance	Summary of Data/Rationale for Risk	Mitigation Strategy
Unknown AEs, laboratory abnormalities, or other safety findings with a novel study drug	This is a first-in-human study with IW-3300 and, as such, there are no clinical data available.	The first cohort will feature sentinel dosing, whereby the first 2 subjects in Cohort 1 will be randomized in a 1:1 ratio to IW-3300 or placebo and dosed at least 4 hours before the remaining subjects in the cohort. Following from there, the study design includes dose escalation to closely monitor subject safety at each dose level before dosing with a higher dose; a Dose Escalation Committee will conduct blinded reviews of all the safety parameters of the dosing cohort through Discharge (Day 2) in order to make decisions regarding escalation to the next dose. Stopping rules are also in place to evaluate continued dosing within a cohort (Section 7.1.1); dosing within a cohort may be temporarily suspended in the event of an SAE considered related to study drug; ≥1 subject with a Grade 3 (severe or medically significant) or higher AE considered related to study drug; or ≥2 subjects with Grade 2 (moderate) or higher AEs considered related to study drug.
Study drug will be administered rectally.	Rectally administered medications may potentially be associated with AEs such as local trauma/discomfort, irritation, or bleeding.	The study excludes subjects for whom rectal administration would be anticipated to be a safety concern. The low-volume enema used in this study is expected to be a lower risk than higher volume enemas. Nonclinical toxicology studies of IW-3300 have shown no signs of local trauma following intrarectal administration.
Study Procedures		
Venipuncture will be performed during the study.	There is the risk of bleeding, bruising, hematoma formation, and infection at the venipuncture site.	Only appropriately qualified personnel will perform the blood draw. Subjects will be monitored for these risks and managed appropriately.

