Section 1.3 (Schedule of Activities/ Table 1) and Section 10.2 (Appendix 2: Clinical Laboratory Tests; Table 2)	
The following laboratory tests were added at Check-in (Day -1) (predose) and Day 2 (Discharge): erythrocyte sedimentation rate (ESR), C-reactive protein (CRP) and hemoccult testing.
 
All laboratory tests will now be analyzed at a local laboratory with the exception of the point-of-care hemoccult tests and the ESR which will be analyzed at an outside laboratory.
 
Because all urine tests will now be analyzed at the local laboratory, the requirement to enter select urine-based screening test results into the CRF was deleted from Table 2.
	
The FDA requested these additional laboratory assessments.
 
The CRU now has the ability to run several laboratory assays locally.
	Substantial
Section 1.3 (Schedule of Activities/ Table 1) and Section 10.2 (Appendix 2: Clinical Laboratory Tests; Table 2)	Alcohol testing at Check-in (Day -1) will be done via a urine test. References to the alcohol screen being done by breath test were deleted.	The CRU now has the ability to do this screen via a urine test.	Substantial
Section 2.3.1 (Risk Assessment, Row # 1: Potential for diarrhea and secondary dehydration)	The Bristol Stool Form Scale (BSFS) score of 7 (watery stools) was added in the evaluation of the severity of diarrhea.	The FDA requested that the definition of diarrhea that would result in temporary dose suspension or trial discontinuation include a criterion for stool consistency as measured by BSFS.	Substantial

Section # and Name	Description of Change	Brief Rationale	Substantial/ Nonsubstantial
Section 5.1.4 (Inclusion Criteria/Sex)	
Inclusion Criterion #7b was removed.
 
Criterion #7a was promoted to Criterion #7.
	
The FDA requested this change. Inclusion Criterion #7b was considered redundant as 1) only women of nonchildbearing potential are eligible for enrollment and these women would not be taking hormonal contraceptives, and 2) subjects who are taking any prescription medications (eg, hormonal contraceptives) are excluded from enrollment as per Exclusion Criterion #5.
	Nonsubstantial

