6.6. Dose Modification

The decision to proceed to the next dose level of IW-3300 (either an increase or a decrease) will be made by the Dose Escalation Committee, based on blinded safety and tolerability data obtained through Discharge on Day 2 in all subjects at the prior dose level.

Dosing at a given dose level may be temporarily suspended for any of the reasons listed in Section [7.1.1](#).

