7.1.1. Study Suspension or Termination

Dosing at a given dose level may be temporarily suspended if any of the following occur within a cohort:

- ≥ 1 subject with an SAE considered related to study drug
- ≥ 1 subject with a Common Terminology Criteria for Adverse Events (CTCAE) Grade 3 or higher AE considered related to study drug (CTCAE v5.0 will be used; grading criteria are summarized in Appendix 3/Section [10.3.3](#))
- ≥ 2 subjects with CTCAE Grade 2 or higher AEs considered related to study drug

The Dose Escalation Committee should consider the benefit-risk ratio in their determination to suspend dosing temporarily or permanently. If the benefit-risk is considered unacceptable and the effect is considered related to active study drug by the Dose Escalation Committee, dosing at a given dose level will be stopped, and no additional cohorts will be dosed at the same or higher dose level (a lower dose could still be studied).

The sponsor may permanently terminate the study, or a component of the study, at any time. Reasons for termination may include, but are not limited to:

- Death, SAE, or other safety finding considered to be related to IW-3300 that may preclude further dosing.

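### Protocol 2.3.1 (diarrhea row) and 7.1.1 give different criteria for suspending dosing, and the stool-count bands in 2.3.1 leave increases above 6 and up to 7 per day in neither grade

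*Protocol*

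**What the plan says.** Protocol 2.3.1, first row (diarrhea and secondary dehydration), cites Section 7.1.1 for its stopping rules and then lists three criteria:

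- An SAE: "dosing within a cohort may be temporarily suspended in the event of a diarrhea or dehydration serious adverse event (SAE").
- At least one subject with "Grade 3 diarrhea (increase from baseline of >7 stools per day", and/or BSFS 7 stools that limit self-care), or with dehydration for which hospital admission is indicated.
- At least two subjects with "Grade 2 diarrhea (increase from baseline of 4 to 6 stools per day", and/or BSFS 7 stools that limit instrumental activities), or with dehydration for which intravenous fluids are indicated.

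None of the three asks whether the event is related to study drug.

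Protocol 7.1.1 also lists three criteria, applied within a cohort: at least one "subject with an SAE considered related to study drug"; at least one subject with a related CTCAE Grade 3 or higher AE; and at least two "subjects with CTCAE Grade 2 or higher AEs considered related to study drug". It says that CTCAE v5.0 applies and refers to Appendix 3 for a summary of the grades. That summary (10.3.3.2) is generic and mentions neither stool counts nor BSFS.

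Protocol 6.6 states: "Dosing at a given dose level may be temporarily suspended for any of the reasons listed in Section" 7.1.1. It does not mention 2.3.1.

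The second row of the 2.3.1 table (unknown AEs) also cites 7.1.1 and keeps the relatedness condition, for example "subjects with Grade 2 (moderate) or higher AEs considered related to study drug".

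The summary of changes for the current amendment explains why the BSFS wording was added: the FDA asked that "the definition of diarrhea that would result in temporary dose suspension or trial discontinuation include a criterion for stool consistency", measured by BSFS.

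**The concern.** The first row of 2.3.1 attributes to Section 7.1.1 a set of criteria that 7.1.1 does not contain. Someone who goes from 6.6 to 7.1.1 and someone who works from 2.3.1 can reach different answers on whether the same diarrhea or dehydration event meets a criterion for suspension. The difference turns on relatedness, which the investigator judges (10.3.3.3) while blinded to treatment (6.3.2).

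The risk table itself describes diarrhea and dehydration as class effects or nonclinical findings, and it offers these rules as mitigation in a first-in-human study. The stool-consistency element that the regulator asked for appears in the risk table but not in the section that 6.6 treats as operative.

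The count bands raise a second, separate problem. One band ends at 6 and the other starts above 7, so some increases belong to neither grade on the count criterion.

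**Working it through.** The plan gives no figure to reproduce here. The check compares the two texts and then does arithmetic on the bands.

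**1. The two lists side by side**

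| Element | 2.3.1, row 1 | 7.1.1 |
|---|---|---|
| SAE | Diarrhea or dehydration SAE, any cause | Any SAE, related only |
| Grade 3 | ≥1 subject, any cause | ≥1 subject, Grade 3 or higher, related only |
| Grade 2 | ≥2 subjects, any cause | ≥2 subjects, Grade 2 or higher, related only |
| Stool count | 4 to 6; >7 | None stated |
| BSFS 7 | Yes | None stated |

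The lists also differ on whether higher grades are named: 7.1.1 names them and row 1 does not.

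**2. Where the lists diverge**

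Take the smallest diarrhea or dehydration pattern that meets each row 1 trigger, vary relatedness, and assume no other qualifying AE in the cohort.

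| Pattern | Meets 2.3.1 row 1 | Meets 7.1.1 |
|---|---|---|
| One SAE, related | Yes | Yes |
| One SAE, unrelated | Yes | No |
| One Grade 3, related | Yes | Yes |
| One Grade 3, unrelated | Yes | No |
| Two Grade 2, both related | Yes | Yes |
| Two Grade 2, one related | Yes | No |
| Two Grade 2, none related | Yes | No |

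All 7 meet row 1, 3 meet 7.1.1, and 7 − 3 = 4 differ.

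**3. Count bands, whole-number increases**

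Increases of 4, 5 and 6 are Grade 2, and 8 or more is Grade 3. An increase of 7 is in neither band. This needs no assumption about how baseline is calculated.

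**4. Count bands, fractional increases**

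Section 2.3.1 does not define its baseline. Assume it is the SAP 9.1 baseline, b/7, where b is the number of BMs in the seven 24-hour periods before dosing. With n stools in the 24 hours after dosing, the increase is n − b/7, and it falls in the gap when

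6 < n − b/7 ≤ 7, that is, 6 + b/7 < n ≤ 7 + b/7.

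This interval has length 1 and is open at one end, so it holds exactly one whole number for any b: n = 7 + floor(b/7). The same argument applies to any other fixed baseline rate.

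Inclusion criterion 3 allows at least 3 BMs per week and at most 3 per day. Taking that as b = 3 to 21 (3 × 7 = 21) gives 19 baseline counts:

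| b (BMs per week) | n in the gap | Increase |
|---|---|---|
| 3 to 6 | 7 | 6.57 down to 6.14 |
| 7 | 8 | 7.00 |
| 8 to 13 | 8 | 6.86 down to 6.14 |
| 14 | 9 | 7.00 |
| 15 to 20 | 9 | 6.86 down to 6.14 |
| 21 | 10 | 7.00 |

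Example: b = 10 gives 10/7 = 1.43 per day, and 8 − 1.43 = 6.57. Three baselines (7, 14, 21) give exactly 7. The other 4 + 6 + 6 = 16 give 6.14 to 6.86.

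**The case against.** **Little turns on it in practice.** Both texts make suspension optional. Section 7.1.1 gives the determination to the Dose Escalation Committee on benefit-risk grounds, immediate concerns go to the sponsor at once (Section 8), and escalation needs a blinded review of the whole cohort whichever list is met. Only Cohort 1 has specified staggering, so for later cohorts the documents fix no interval in which a within-cohort suspension would act. All of this stands and limits the consequence. It does not settle which events meet a criterion.

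**Row 1 may only summarize 7.1.1 for one risk, with relatedness implied.** Section 7.1.1 is generic and does cover any related diarrhea or dehydration AE of sufficient grade. But row 2 of the same table makes relatedness explicit under the same citation. If row 1 is instead an additional diarrhea rule, 7.1.1 and 6.6 omit it. Neither reading removes the conflict.

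**CTCAE v5.0 may supply the missing definitions.** Its diarrhea-specific text is not in the documents, so it was not used here. A case in the gap would still be graded through 7.1.1 and Appendix 3, could count there if related, and might qualify through the watery-stool branch of row 1. That stands. The gap concerns the count criterion only.

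**The amendment log records the BSFS change in 2.3.1, where it appears.** This is correct. The rationale is evidence of purpose only, and the finding does not depend on it.

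**The figures rest on construction and assumption.** The seven patterns are built from row 1's triggers, so all meet row 1 by design and 4 of 7 is no estimate of frequency. The eligibility window (Days -8 to -2) differs from the SAP baseline window, and Protocol 9.4.4 defines a third period, up to randomization. So 3 to 21 does not strictly bound b, and the 19 baselines are illustrative. The result of one stool count in the gap for any fixed baseline does not depend on that range.

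**Conclusion.** The concern holds and should be fixed. The first row of 2.3.1 and Section 7.1.1 state different criteria for possible suspension under one citation. They disagree for an unrelated diarrhea or dehydration SAE, for an unrelated Grade 3 case, and for two Grade 2 cases of which at most one is related (4 of the 7 patterns, as an illustration). This follows from the text alone.

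The gap at an increase of exactly 7 also follows from the text alone. The wider gap, above 6 and up to 7, matters in practice if baseline is a fractional daily rate as in SAP 9.1, which 2.3.1 does not state. The documents give no frequency for either kind of case. Because suspension is discretionary and every escalation is reviewed separately, this is a conflict in decision criteria and does not show that dosing would continue unsafely.

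**What to change.** Reconcile Protocol 2.3.1, 6.6, 7.1.1 and 10.3.3.2 so that the operative section holds a single set of suspension criteria. It should:

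- state one position on whether relatedness is required for diarrhea and dehydration events;
- carry one stool-count and BSFS wording, used identically wherever it is repeated;
- say whether each grade criterion includes higher grades;
- define the baseline from which the count increase is measured;
- word the bands so that every increase at or above the lowest threshold, including fractional values, falls in exactly one grade.

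Which thresholds and conditions apply is the sponsor's medical decision; this review does not propose any. The cost is a short clarification of protocol text, with no extra data or procedures.

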2.3.2. Benefit Assessment

Benefits to individual subjects may include:

- Medical evaluations/assessments associated with study procedures (eg, physical examinations, ECGs, laboratory evaluations, SARS-CoV-2 (COVID-19) diagnostic testing)
- Contributing to the process of developing new therapies in an area of unmet need

2.3.3. Overall Benefit: Risk Conclusion

Taking into account the measures taken to minimize risk to subjects participating in this study, the potential risks identified in association with IW-3300 are justified by the anticipated benefits.

3. OBJECTIVES AND ENDPOINTS

3.1. Objectives

3.1.1. Primary Objective

The primary objective is to assess the safety and tolerability of single ascending doses of IW-3300 administered rectally via enema in healthy volunteers.

3.1.2. Exploratory Objectives

The exploratory objectives are:

- To summarize the single-dose PK of IW-3300 administered rectally via enema in healthy volunteers
- To summarize the single-dose PD of IW-3300 administered rectally via enema in healthy volunteers based on bladder and bowel assessments

3.2. Estimands

Not applicable for this Phase 1 study.

3.3. Endpoints

3.3.1. Primary Endpoints (Safety)

The primary endpoints are:

- Incidence of TEAEs
- Incidence of TESAEs

3.3.2. Exploratory Endpoints (Pharmacokinetics and Pharmacodynamics)

The exploratory endpoints are:

- PK parameters
- Total amount of IW-3300 in stool (concentration and percent recovery)
- Change from baseline in BM frequency during the Clinic Period
- Change from baseline in stool consistency (BSFS score) during the Clinic Period
- Change from baseline in urinary frequency during the Clinic Period for a 24-hour duration
- Change from baseline in urinary urgency during the Clinic Period for a 24-hour duration
- Change from baseline in nocturia during the Clinic Period for a 24-hour duration
- Change from baseline in pain or burning in bladder or pelvic area during the Clinic Period for a 24-hour duration

4. STUDY DESIGN

4.1. Overall Design

This is a Phase 1, single-center, randomized, double-blind, placebo-controlled, single-ascending-dose study assessing the safety, tolerability, and PK of IW-3300 administered rectally as a low-volume enema in healthy adult volunteers. Each cohort will progress through 3 study periods: (1) Screening Period, (2) Clinic Period, and (3) Follow-up Period; these periods and the progression between cohorts are illustrated in the study schematic ([Figure 1](#)).

This first-in-human study in healthy adult volunteers will assess all subjects for safety, PK, and effect on stool frequency/form and urination.

The study will include up to 5 cohorts with 8 subjects per cohort; within each cohort, subjects will be randomized to receive a single dose of IW-3300 (6 subjects) or placebo (2 subjects), administered rectally (as detailed in Section [6.1.1](#)). The planned cohorts are:

- Cohort 1: 100 µg IW-3300 or matching placebo single rectal dose
- Cohort 2: 300 µg IW-3300 or matching placebo single rectal dose
- Cohort 3: 900 µg IW-3300 or matching placebo single rectal dose
- Cohort 4: 2500 µg IW-3300 or matching placebo single rectal dose
- Cohort 5 (optional): ≤ 2500 µg IW-3300 or matching placebo single rectal dose (specific dose level to be determined after safety reviews of previous cohorts; doses higher than 2500 µg will not be tested)

In Cohort 1 only, sentinel dosing will be implemented. If no safety signals are noted in the first 2 subjects (randomized 1:1 to IW-3300 or placebo) following an observation period of at least 4 hours postdose, the remaining 6 subjects in Cohort 1 will be dosed. For all subsequent cohorts, a Dose Escalation Committee will conduct blinded reviews of all the safety/tolerability parameters through Discharge (Day 2) from the prior dosing cohort in order to make decisions regarding dose escalation. The Dose Escalation Committee will include sponsor and CRO representatives. Dose escalation is detailed in Section [6.6](#).

4.1.1. Study Periods

4.1.1.1. Screening Period

The Screening Period will begin with the signature of the informed consent form (ICF) at the Screening Visit (which can occur from Day -28 to Day -8) and will last 7 to 27 days. At the Screening Visit, subjects will undergo preliminary screening procedures to ensure that they meet the inclusion and exclusion criteria for the study. Eligible healthy volunteers will receive the bladder and bowel movement diary (BBMD), a paper-based diary to complete on an event-driven basis (ie, for each BM) at home, and training on how to complete it to record their bladder and bowel habits. Subjects will complete the BBMD (BM portion only) daily only for the 7 days before Check-in on Day -1. The end of the Screening Period will coincide with the beginning of the Clinic Period at Check-in (Day -1).

4.1.1.2. Clinic Period

The Clinic Period will begin at Check-in to the Phase 1 CRU on Day -1 (the day before dosing), and will end at the time of Discharge on Day 2 (the day after dosing). Following confirmation of eligibility at Check-in, subjects will be admitted to the CRU and will undergo baseline procedures. On the morning of Day 1 (note that there is no Day 0), subjects in each cohort will undergo predose assessments and will be randomized in a 3:1 ratio to receive IW-3300 or matching placebo after a fast of at least 6 hours. In Cohort 1 only, the first 2 subjects will be randomized in a 1:1 ratio to IW-3300 or placebo and dosed at least 4 hours before the remaining subjects in the cohort.

Blood and stool samples for PK assessments will be collected at specified times predose (blood) and postdose (blood and stool) during the Clinic Period (see SoA in [Table 1](#)). Throughout the Clinic Period, safety assessments will be performed and subjects will continue to enter their BM information into the BBMD on an event-driven basis. Bladder and urination information in the BBMD will be collected on Day 1 predose and Day 2, with a 24-hour recall period at each timepoint. Subjects will be confined to the CRU from Check-in (Day -1) through 1 day of dosing until Discharge (Day 2), which will occur after completion of the assessments (at least 24 hours after administration of study drug) and at the investigator's discretion.

4.1.1.3. Follow-up Period

The Follow-up Period will start immediately after subjects are discharged from the Phase 1 CRU on Day 2 and will last for 12 (+3) days. At the conclusion of the Follow-up Period (Day 14+3), the Phase 1 CRU will contact subjects for the Follow-up Phone Call (at the discretion of the investigator, subjects may be requested to return to the Phase 1 CRU for their follow-up contact). The Follow-up Phone Call will be considered the end of the study for that subject.

4.2. Scientific Rationale for Study Design

A randomized, double-blind, placebo-controlled study design was chosen to investigate the safety, PK, and PD of IW-3300, and to determine the tolerability of a range of doses of IW-3300 administered rectally as a low-volume enema. Subjects will be randomized within each cohort to ensure that the treatment groups are comparable and to minimize the potential for selection bias. The study will be double-blind to ensure that the subjects and CRU staff are unaware of the treatment assignment and to minimize the potential for bias in study assessments or AE reporting. Placebo was chosen as the control so that the rate of spontaneously occurring AEs can be determined and to reduce the potential for bias in the reporting of AEs.

Subjects will complete the BM portion of the BBMD during the last 7 days of the Screening Period to establish a baseline without study drug. Subjects will be confined to the CRU for the duration of the Clinic Period, from Check-in (Day -1) through 1 day of dosing until Discharge (Day 2), which will occur after completion of the assessments (at least 24 hours after administration of study drug) and at the investigator's discretion. CRU staff will contact subjects for the Follow-up Phone Call 12 (+3) days after Discharge for safety follow-up; at the discretion of the investigator, subjects may be requested to return to the CRU for their follow-up contact.

Because this is the first-in-human study with IW-3300, Cohort 1 will feature sentinel dosing whereby the first 2 subjects will be randomized in a 1:1 ratio to receive IW-3300 or placebo, and

[figure not shown]
they will be dosed at least 4 hours before the remaining subjects in the cohort. Subsequently, the cohorts will be enrolled sequentially, following a safety review of prior dosed cohorts. In addition, stopping criteria have been established to ensure that dosing at the same or higher dose levels (a lower dose could be used) will stop should a safety signal be detected.

